5.3 Pharmacokinetics and Pharmacodynamics Variables

Blood samples for pharmacokinetic (PK) analysis will be collected prior to dosing at Baseline, Months 3, 6, and at Early Termination.

All participants with at least one dose of study medication will be included in the pharmacokinetic and pharmacokinetic/pharmacodynamic analyses, as appropriate.

5.4 Adverse Events of Special Interest

Adverse events related to signs and symptoms of AD potentially pertain to efficacy as well as safety of the compound. Descriptive analysis will include TEAEs classified by MedDRA into the SOC for psychiatric disorders (at the SOC level within the hierarchy of MedDRA) and high level group terms (HLGTs) of anxiety disorders and symptoms (at the HLGT level within the hierarchy of MedDRA).

Standardized MedDRA queries (SMQs) will be used for dynamic analysis of any TEAE that emerges of potential interest.

Conditions associated with substance abuse are included in the SOC Psychiatric Disorders in high level term (HLT) “Substance-related disorders,” which will be used for identification of terms pertaining to substance abuse. Variables of interest will include incidence estimates for each treatment group for the HLT and PTs within the HLT. It is noted that terms that refer to a person as a “drug abuser” would be captured in the SOC Social Circumstances, which is not intended for contributing to variables of analysis.

6 Statistical Methodology

General statistical methods will be applied as appropriate for out-patient clinical studies. Safety evaluations will rely on descriptive statistics. Randomization groups will be examined for homogeneity between treatment groups.

Continuous variables will be summarized using mean, median, standard deviation, minimum, maximum, and number of subjects available for analysis. Categorical variables will be summarized using frequency, proportion, and number of subjects available for analysis.

SAS version 9.3 or later will be used.

6.1 Pooling of Investigator Sites

Pooled sites will not be included in the model due to small N overall.

6.2 Statistical Methodology for Efficacy Analysis

The primary analysis will use the ITT methodology and a mixed-model measures (MMRM) methodology with a random slope and intercept for each individual. The MMRM will utilize an

unstructured covariance with only one parameter for the correlation between the slope and intercept. Time (ADY) is considered as a continuous variable. Analysis will include baseline risk score, treatment, time, as well as HbA1C by treatment, treatment-by-time, baseline by treatment, and baseline by time interactions as fixed effects. Subject will be included as a random effect. Baseline visit will be included in the model. Baseline risk score is derived from the historic STEADFAST data and calculated as a linear calculation of:

$$age*-0.03582 + hba1c*-0.2335 + mmsebl*-0.2683 + base*-0.09342$$

First the baseline risk score will be subtracted from the change score for each individual. Then the mean baseline value of the risk adjusted change score will be calculated separately for each treatment group. Finally, the risk adjusted change scores for each individual will have their group mean added back in to ensure an average score of 0 at baseline for each group. This adjusted change score will be used in the model in place of change from baseline. Model assumptions will be evaluated. If the parametric assumptions are evaluated as inappropriate or violated, rank analogues will be advanced.

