9.7.2 Statistical Methodology for Primary Analysis

The primary analysis will use the ITT methodology and a main-effects mixed-models for repeated measures (MMRM) methodology. The MMRM will utilize an unstructured covariance where the number of parameters is “ $t(t+1)/2$ ” where “ t ” is the dimension of the covariance matrix, using PROC MIXED in SAS. In the unlikely event of lack of convergence, Toeplitz structure will be employed where the number of parameters is “ t ” where “ t ” is the dimension of the covariance matrix. Time is considered as a class variable. Analysis will include treatment, time and treatment-by-time interaction as fixed effects, Baseline as covariate, and subject as a random effect. Supportive modeling will also include MMRM main-effects model with treatment, time, and subject.

Model assumptions will be evaluated. If the parametric assumptions are evaluated as inappropriate or violated, rank analogues will be advanced.

The primary analysis will be done for each stage separately. Part 1 will use alpha = 0.0499, which includes an adjustment of 0.0001 for interim analyses performed by the Independent Data Monitoring Committee (IDMC). The alpha adjustment for the IDMC for Part 1 is considered to be negligible, hence, the stated alpha for Part 1 is 0.05 for the 100-patient, 6-month trial. Part 2 will use alpha = 0.049, which includes an adjustment of 0.001 for interim analyses performed by the Independent Data Monitoring Committee (IDMC), thereby preserving the overall study-wise alpha = 0.05. The alpha adjustment of 0.001 is considered to be appropriate for the 200-patient, 18-month study.

Multiple imputations (MI) will be used as a supportive analysis with 100 invocations (acknowledging that more invocations are needed with more missing data). Monte Carlo methods are planned.

An essential component of the thorough analysis includes an assessment of the impact of missing data on study conclusions. As a part of assessing this impact, supportive analysis will include:

- an endpoint analysis (reduction to last-observation-carried-forward, justified in this study based on the monotonic progression of the natural course of AD and assuming no more dropouts in the group treated with azeliragon than in the group treated with placebo)
- a completers analysis (observed cases at endpoint)
- observed cases by assessment time.

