* ADAS-Cog will also be run using LZCF. If neither of these are significant, the cognitive composites and global statistical test (GST) will be assessed for significance to demonstrate proof of concept. It is acknowledged that the present study is underpowered to replicate the clinically meaningful effect size observed in the STEADFAST combined A- and B-study diabetes subgroup. Therefore, if the observed effect size (treatment difference) or percent slowing (treatment difference divided by the placebo change) is equal to or greater than the corresponding values from the STEADFAST pooled analysis (-0.92; -61%), this will be considered proof of concept. Lack of strict statistical significance is expected with this range of effect size due to the small n, but this result, in the context of the consistency of the effect seen in STEADFAST Part A with the STEADFAST Part B data would provide proof of concept for this compound.

§ All secondary variables will also be run using LZCF.

3 Estimand Specification

This SAP is constructed to conform to regulatory guidance. In particular, this section is included as recommended by ICH E9 (R1) Addendum on estimands and sensitivity analysis in clinical trials to the guideline on statistical principles for clinical trials (30 August 2017).

In accordance with ICH E9 Addendum, the specification of the estimand is included in this SAP with the 4 attributes detailed in ICH E9 Addendum, Section A.3.1:

- A. The Population, that is, the subjects targeted by the scientific question:
For this study, the population consists of subjects with AD and HbA1c of 6.5% - 9.5% who meet eligibility requirements for the study, receive double-blind medication, and have at least one valid post-baseline measure of ADAS-cog(14).
- B. The variable (or endpoint) to be obtained for each patient, that is required to address the scientific question:
For this study, the primary endpoint is Change in ADAS-cog(14).
- C. The specification of how to account for intercurrent events to reflect the scientific question of interest:
Due to the small sample size intercurrent events will not be accounted for in this analysis.
- D. The population-level summary for the variable that provides, as required, a basis for a comparison between treatment conditions:
For this study, the population-level summary for the variable is the least-squares mean (LSM) of the treatment difference in mean change from baseline in ADAS-cog(14).

4 Populations of Analysis

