5.1.1 Primary Efficacy Variable

The primary analysis will include assessment of the following variables.

- Mean change from Baseline to Month 6 in ADAS-cog14*

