5.1.5 Efficacy Scales

Generation of instrument total scores will be calculated from individual items. The following instruments that are used in this study are subject to statistical analysis:

5.1.5.1 Alzheimer's Disease Assessment Scale - Cognitive Subscale 90 point (ADAS-cog):

- Range: The scale range is 0 to 90 with higher scores indicating greater cognitive impairment.
- Brief description: The 14-Item Alzheimer's Disease Assessment Scale - Cognitive Subscale (ADAS-cog14) is a structured scale (approximately 45 minutes to complete) that evaluates memory, orientation, attention, reasoning, language, constructional praxis, delayed recall, digit cancellation, and maze-completion. The ADAS-cog14 scoring range is from 0 to 90, with higher scores indicating greater cognitive impairment (Mohs et al. 1997). The ADAS-Cog should always be administered prior to other cognitive measures. The ADAS-Cog will be administered at Screening, Baseline, Months 3 and 6 or in the event of early termination. Participants must have scores of ≥ 10 at Screening and Baseline to be eligible for participation in the study.

5.1.5.2 Mini Mental State Examination (MMSE):

- Range: The scale range is 0 to 30 with lower scores indicating greater cognitive impairment.
- Brief description: The MMSE is a brief 30-point test that is used to assess cognition (Folstein, 1975). It is commonly used to screen for dementia. In the time span of about 10 minutes, it samples various functions, including arithmetic, memory and orientation. The MMSE will be administered at Screening, Baseline, Months 3 and 6 or in the event of early termination. Participants must have scores of 21-26 at Screening and 19-27 at Baseline to be eligible for participation in the study.

5.1.5.3 Functional Activities Questionnaire (FAQ):

- Range: The score ranges from 0 to 30. Higher scores are associated with greater impairment.
- Brief description: The FAQ is an inventory of instrumental activities of daily living developed by (Pfeffer 1982). The FAQ is administered by asking the informant to rate patient's ability (0-3) on 10 different activities of daily living. The FAQ will be administered at Screening, Baseline, Months 3 and 6 or in the event of early termination.

5.1.5.4 Amsterdam-Instrumental Activities of Daily Living Questionnaire (A-IADL):

- Range: scoring range from 20 to 80, with lower scores indicating greater impairment.

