8.1 Definition of Baseline

For safety evaluations, the Baseline assessment for all measurements will be the latest available, valid measurement taken prior to the initiation study medication, except for electrocardiography (ECG) values: The Baseline assessment for ECG include a triplicate assessment with the baseline value intended to be the arithmetic mean of the values taken at the Baseline assessment that are taken in triplicate. Baseline values for efficacy outcomes will be the average of screening and baseline visits where available. For the GST, the z-scores at each visit will be calculated using the mean over all patients of the average of screening and baseline, and using the standard deviation pooled across screening and baseline.

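### SAP 6.2 fits a straight line in study day to a Month 6 endpoint, so the Month 6 estimate leans on Month 3: with complete data read at Day 180 it is off by 0 to about 17%, depending on an unknown effect shape, for essentially no gain in precision

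*SAP*

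**What the plan says.** SAP 5.1.1 defines the primary variable as "Mean change from Baseline to Month 6 in ADAS-cog14". On the visits, SAP 5.1.5 states: "The ADAS-Cog will be administered at Screening, Baseline, Months 3 and 6 or in the event of early termination".

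Protocol 9.7.2 describes a repeated-measures model with unstructured covariance and says "Time is considered as a class variable". SAP 6.2 replaces this with a model "with a random slope and intercept for each individual", in which "Time (ADY) is considered as a continuous variable" and "Baseline visit will be included in the model". Treatment and treatment-by-time are fixed effects. The outcome is a risk-adjusted change score, shifted so that each arm averages zero at baseline. SAP 8.1 adds: "Baseline values for efficacy outcomes will be the average of screening and baseline visits where available".

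SAP Sections 3 and 6.6 summarise the comparison as a least-squares mean difference and give no day at which it is evaluated. SAP 1.9 names several modifications to the protocol's statistical section. The move from categorical to linear time is not among them.

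**The concern.** The question asked is about one time point. A straight line answers it by pooling three time points under an assumed shape, so the Month 3 result moves the Month 6 estimate. Three visits leave little room to notice if the shape is wrong.

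The size of the estimate matters here beyond the p-value. SAP Section 2 accepts proof of concept on effect size alone, without significance (-0.92, or 61% slowing). If -0.92 is the bar on this scale, which the SAP leaves unclear, a true Month 6 difference of 0.92 / 1.167 = 0.79 would reach it when the whole effect is present by Month 3. A difference of 0.92 / 0.833 = 1.10 would be needed when the effect appears only afterwards.

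**Working it through.** **The plan's own figure.** The documents give no number for the choice between line and class visit. The nearest is the recalculated power in SAP 1.6: N = 43, SD 3.4, difference 1.54, two-sided 0.05, power 30%, expected p 0.144. With 21 and 22 patients, SE = 3.4 × √(1/21 + 1/22) = 1.037 and t = 1.54 / 1.037 = 1.485. This gives p = 0.145 and power 30.5%, so the figure reproduces and 1.54 is a fair scale for what follows.

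**Weights of the line.** Write D0, D3 and D6 for the treatment differences at Months 0, 3 and 6. With equally spaced visits and complete data, the fitted value at Month 6 is

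-1/6 × D0 + 1/3 × D3 + 5/6 × D6 = 5/6 × D6 + 1/6 × (2 × D3 - D0).

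The bracket is the Month 0-to-3 trend extrapolated to Month 6. In balanced complete data the same weights hold for any random intercept and slope covariance; this was confirmed numerically. Because SAP 6.2 centres each arm at zero at baseline, D0 = 0. If a share s of the Month 6 effect is present at Month 3, the fitted value is (s/3 + 5/6) times the true Month 6 effect.

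| Share at Month 3 | Multiple of truth | Shift on 1.54 points |
|---|---|---|
| 0% | 0.833 | -0.26 |
| 25% | 0.917 | -0.13 |
| 50% (linear) | 1.000 | 0 |
| 75% | 1.083 | +0.13 |
| 100% | 1.167 | +0.26 |

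The largest shift, 1.54 / 6 = 0.26, is 0.21 of the simulated SE of 1.25 given below, or 0.25 of the 1.037 above.

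**Dropout.** With 18% of Month 6 values missing (the planning rate, assumed completely at random), the extremes become 22-27%. With 30% missing they become 27-34%. The ranges reflect variance components that the documents do not give; visit noise was varied from 30% to 90% of the Month 6 change variance.

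**Other contrasts.**
- Slope × 180 days has weights -1, 0, +1. Distortion is zero with complete data and about 7-12% with 18% dropout.
- With no treatment intercept, the weights are 0, 0.4, 0.8, and the extremes are 20% off.
- A mean difference read at the average study day, (0 + 90 + 180) / 3 = Day 90, would be about half the Month 6 effect even if the line were true.

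**Precision.** The SE of the line was compared with that of class visit under random slope plus visit noise, with the noise share varied from 10% to 100% (an assumption).
- Complete data: the ratio is 0.994 to 1.000 with the averaged baseline and 1.003 to 1.041 with a single baseline.
- 18% dropout: the SE changes by -1.3% to +4.3%.
- 30% dropout with the averaged baseline: the line is at best about 3% tighter.

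A simulation (43 patients, SD 4, 18% dropout, 220 replicates per shape) gave mean SEs of 1.25 for the line, 1.22 for class visit and 1.28 for a line with a Day 90 knot. The line and class-visit estimates differed by 0.24 for an early effect (-1.84 v -1.60) and by 0.34 for a late one (-1.37 v -1.71). The run is small, with Monte Carlo error of about 0.08 per mean. The algebra carries the point.

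**Shape in the previous studies** (Protocol 1.1.3).
- A-study subgroup (17 v 7): 3.8 points at Month 6 and 6.1 at Month 18. A line to Month 18 implies 6.1 × 6/18 = 2.0 at Month 6.
- B-study subgroup (13 v 13): 1.9 at Month 6 and 3.6 at Month 12. A line implies 3.6 × 6/12 = 1.8.

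**The case against.** The change is permitted: Protocol 9.0 lets the SAP supersede it. That stands, but permission is not disclosure, and SAP 1.9 is where a new form for the primary model belongs.

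Actual study day has a real benefit. SAP Section 7 expects some endpoint visits after Month 6 because of COVID-19, and class visit would label those as Month 6. This stands and is the reason to offer a knot version. The precision figures above do not cover mistimed visits.

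SAP Section 7 also calls multiple imputation of Month 6 the primary analysis and MMRM supportive. Whether the line is the final primary estimator is therefore unsettled within the SAP itself.

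The protocol is not a clean model to return to. Its synopsis makes ANCOVA with multiple imputation primary. Section 9.7.2 lists treatment-by-time and later says the primary model has no interaction terms. A class-visit model without that interaction averages Months 3 and 6: with equal weights, a purely late effect would read (0 + 1)/2 = 0.5 of the truth, worse than the line.

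Partial safeguards exist: by-visit descriptives, observed cases by assessment time, and a check of assumptions. None is a named categorical-time model, and the stated fallback to rank methods does not address a wrong time shape.

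A reader might infer from the A-study that linearity has been refuted. It has not. Back-calculating from p = 0.009 (assuming a t-test on 22 df) gives a Month 6 interval of about 1.0 to 6.6, which contains 2.0. The B-study is close to linear. Curvature between Months 6 and 18 says little about Months 0 to 6, and the Month 3 values are in a figure not reproduced in the text available here.

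**Conclusion.** The point holds as an undeclared shape assumption in the Month 6 estimate, with an unnamed contrast day. With complete, on-schedule data read at Day 180, the error is nil for a linear effect, about 8% at the quarter points and at most about 17% at the extremes. Dropout makes it larger.

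Two stronger readings are tempting. One is that the estimate will be 17% wrong. That requires all or none of the effect by Month 3 and a Day 180 reading that the SAP does not state. The other is that false positives rise. With no effect at any visit, these weights return zero, so the type I error is not affected by this weighting.

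What remains is a modest, avoidable dependence on an assumption that buys essentially no precision across the variance components tried. It should be changed, but it does not by itself undermine the trial.

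**What to change.** For the primary Month 6 contrast, choose one of two forms:

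- **Class visit with treatment-by-visit.** State the interaction explicitly, because Protocol 9.7.2 can be read as excluding it.
- **Study day with a knot at Day 90 and treatment-by-knot**, if actual timing is to be kept for COVID-delayed visits.

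In either case, name the contrast as the least-squares mean difference at Month 6 (Day 180), keep the straight-line model as supportive, reconcile SAP 6.2 with SAP Section 7 on which analysis is primary, and add the change with its reason to SAP 1.9.

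The cost is SAP wording. In the simulation the knot version's SE was about 2% above the line's (1.28 / 1.25) and about 5% above class visit's (1.28 / 1.22). Class visit did not widen the SE relative to the line (1.22 v 1.25).

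### The add-back step in SAP 6.2 cannot give the baseline average of 0 it promises, and its arm-specific constant moves the LSM treatment difference

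*SAP*

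**What the plan says.** SAP 6.2 builds the primary outcome in three steps:

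1. "First the baseline risk score will be subtracted from the change score for each individual".
2. "Then the mean baseline value of the risk adjusted change score will be calculated separately for each treatment group".
3. The individual scores "will have their group mean added back in to ensure an average score of 0 at baseline for each group".

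The result replaces change from baseline as the modelled response. The risk score is "age*-0.03582 + hba1c*-0.2335 + mmsebl*-0.2683 + base*-0.09342", with coefficients taken from the earlier STEADFAST studies. The fixed effects already contain both the risk score and treatment: "Analysis will include baseline risk score, treatment, time, as well as" several interactions. The same section also says "Baseline visit will be included in the model".

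SAP 8.1 adds: "Baseline values for efficacy outcomes will be the average of screening and baseline visits where available". SAP 5.1.5 has the ADAS-cog given at both of those visits ("The ADAS-Cog will be administered at Screening, Baseline, Months 3 and 6 or in the event of early termination").

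SAP 6.2 does not say which model contrast is tested. The estimand in SAP 3 (attribute D) and the reporting rule in SAP 6.6 are both LSM differences. Protocol 9.7.2 has no risk-score or add-back step.

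**The concern.** There are two separate faults.

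- **The instruction contradicts its own purpose.** Step 2 defines the mean as that of the risk-adjusted score. Adding that mean to scores that already average to it doubles the average; it does not remove it. Programmers who follow the words and those who follow the purpose would derive different primary outcome variables.
- **The constant differs by arm.** Even with the sign corrected, each arm receives its own constant in a model that already adjusts for the risk score. Chance imbalance between the arms in mean risk score is then written into the treatment effect, and the model standard error does not count it.

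The quantity at risk is the LSM difference that the SAP says it will report. The footnote to SAP 2 also lets the observed treatment difference alone establish proof of concept, so a displaced point estimate matters apart from the p-value. Percent slowing is exposed only if LSM levels of the outcome as written are used as the placebo change.

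**Working it through.** **Inputs from the documents.** Risk-score coefficients: SAP 6.2. Eligibility minimums: age 50, HbA1c 6.5%, baseline MMSE 19, ADAS-cog14 10 (SAP 1.3). N = 43, allocated 1:1 (SAP 1.4), taken as 22/21. ADAS-cog14 SD of 4 and design difference of 2.9; ADAS-Cog11 SD of 3.4 and effect of -1.54 (SAP 1.6). Alpha 0.0499 (SAP 6.6).

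**Step 1: can the stated average of 0 be reproduced?** Let C be change from baseline, R the risk score and A = C - R. Let m be an arm's mean of A at baseline. If C = 0 at baseline, m = -Rbar for that arm.

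- As written, the outcome is A + m, with baseline average 2m = -2 Rbar.
- With the mean subtracted, the outcome is A - m, with baseline average 0.

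All four coefficients are negative, so -R is smallest at the eligibility minimums:

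0.03582 × 50 + 0.2335 × 6.5 + 0.2683 × 19 + 0.09342 × 10 = 1.791 + 1.518 + 5.098 + 0.934 = 9.34

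The average as written is therefore at least 2 × 9.34 = **+18.7**, not 0. HbA1c is restricted only at screening; leaving that term out still gives 2 × 7.82 = +15.6. The averaged baseline of SAP 8.1 cannot rescue the rule, because the mean change in the baseline row would have to be about -9 points or beyond.

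**Step 2: what reaches the treatment term?** The outcome is C - R + k, where k is constant within an arm. R is a fixed effect, so its coefficient absorbs -R. Treatment is a fixed effect, so it absorbs the arm difference in k. Write D for Rbar(active) - Rbar(placebo), and d0 for the arm difference in mean change in the baseline row.

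| Baseline row | LSM shift, as written | LSM shift, mean subtracted |
|---|---|---|
| exactly 0 | -D | +D |
| not 0 | d0 - D | D - d0 |

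The treatment-by-time slope and a Month 6-minus-baseline contrast do not move. Fits of the 6.2 model to simulated 43-patient data sets agreed with this. In one set the arm difference in m was -0.1859; the LSM difference moved by -0.1859 as written and +0.1859 with the mean subtracted, and the slope was identical.

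**Step 3: size with the baseline row at 0.** The documents give no baseline SDs, so these are assumptions: age 6-9, HbA1c 0.5-0.8, MMSE 1.5-2.2, ADAS-cog14 5-8.5, MMSE/ADAS-cog correlation -0.6 to -0.2. They give SD(R) of 0.46-0.97, rounded to 0.5-1.0.

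- Shift SD = SD(R) × sqrt(1/22 + 1/21) = SD(R) × 0.305 = 0.15-0.31 points, with mean 0.
- 95% range = 1.96 × that = ±0.30 to ±0.60. This outer edge is 10-21% of 2.9, or 19-39% of 1.54 (an ADAS-Cog11 figure, so indicative only). One SD is about 5-11% of 2.9.
- A wider set of assumed SDs gives SD(R) of 0.56-1.21 and a shift SD of 0.17-0.37.
- Type I error of the LSM test by formula, 2 × (1 - Phi(z / sqrt(1 + (SD(R)/SD)²))): 5.2-5.7% with SD 4, and 5.2-6.0% with SD 3.4 as a stand-in.

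**Step 4: simulation of the 6.2 model.** 6,000 trials of 43 patients per setting; Months 0, 3 and 6; complete data; REML with random intercept and slope; SD 4; Month 6 LSM difference at mean covariates; t critical value with 36 df; Monte Carlo SE about 0.3-0.4 percentage points. For the non-zero baseline row, the SD of the screening-to-baseline difference was assumed to be 2-4 points, which gave a shift SD of 0.34-0.69.

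| Baseline row | Plain change | As written | Sign corrected |
|---|---|---|---|
| 0 | 4.7-4.9% | 4.5-5.1% | 4.8-5.2% |
| not 0 | 4.6-5.7% | 5.3-8.5% | 5.7-10.0% |

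The slope test stayed at 3.6-4.2% throughout. Standard errors are the same for all three outcomes, because an arm constant does not change the REML variance estimates; only the estimate moves.

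No comparison is made with the -0.92 threshold in the footnote to SAP 2. SAP 1.6 gives that figure for the z-score composite, so its unit there is unsettled.

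**The case against.** The strongest reply is that the intent is plain. The sentence states its target of 0, and the phrase about adding back could mean the arm mean of the risk score that was subtracted, which does give 0 when baseline change is 0. A programmer who checks the stated property would catch the error. The +18.7 level is also largely common to both arms and so does not itself move the treatment difference. All of this is fair as to intent. It does not make the text right: the preceding sentence defines a different mean, and the charitable reading leaves the same arm-specific constant and the same shift of +D.

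The second reply concerns weight. The shift averages zero over randomizations, so it is not systematic bias. A slope-type test would be untouched, and continuous time with random slopes is compatible with one. With the baseline row at 0, the simulated change in type I error is at most about 0.4 percentage points, within simulation noise. The row would be 0 if it carries the averaged baseline value itself. The larger figures rest on assumed SDs. These points stand and limit the second fault. They do not remove it, because the SAP names neither the contrast nor the handling of the baseline row, and its estimand and reporting rule are LSM differences.

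**Conclusion.** The concern holds.

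- **Certain from the text:** the derivation rule for the primary outcome cannot deliver its stated baseline average. With baseline change 0, it gives at least +18.7 where the SAP promises 0.
- **Certain from the model specification:** with risk score and treatment both as fixed effects, an arm-specific constant passes one for one into the LSM treatment difference, whichever sign is used.
- **Conditional:** the practical effect depends on the LSM difference being the tested or reported quantity. With the baseline row at 0 it is modest: a shift SD of 0.15-0.31 points under the assumed SD(R) of 0.5-1.0, and little change in type I error. If averaging screening and baseline leaves that row non-zero, type I error could be about 5.3-10.0%, under an assumed visit-to-visit difference SD of 2-4 points.

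The step should be corrected. It adds avoidable noise to a 43-patient comparison and gains nothing, since the risk score is already a covariate.

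**What to change.** Replace the derivation paragraph in SAP 6.2 as follows.

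- Model plain change from baseline with the risk score as a covariate. Equivalently, centre the risk score at one mean pooled over both arms, never at arm-specific means. The treatment estimate then equals the plain covariate-adjusted estimate.
- Name the Month 6 contrast that is tested.
- State whether change in the baseline row is set to 0 under the averaged baseline of SAP 8.1.
- State that the placebo change used for percent slowing comes from unshifted change scores.
- State whether the risk-score step carries over to the secondary scales, for which SAP 6.7 promises only similar methodology. If it does, apply the same rule there.

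The cost is one paragraph of SAP text and simpler code. No new data are needed.
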